So, the relative increase in variance due to missing values is 32%, indicating that $1.32 * 180$ subjects = 238 subjects are required to attain the same power that would be attained in a sample of 180 subjects who all complete the study. In other words, 238 subjects must be enrolled in the study, with 180 completing, to achieve the same power when using multiple imputation as would be achieved if 180 subjects were enrolled and all completed. If multiple imputation were not used, and only complete cases were analyzed, approximately 238 subjects would have to be enrolled to produce 180 complete cases. Thus, multiple imputation is more efficient than complete-case analysis, in addition to avoiding bias due to MAR missingness.

A secondary analytic approach will be to use mixed models on non-imputed data. Mixed models can be used to analyze repeated measures data without discarding subjects with missing data. Mixed models will be used for measures only obtained at pre- and post-assessment and on measures with interval assessments. Analytic approaches for each set of specific aims and hypotheses are detailed below.

Specific Aim 1: To conduct an RCT of an early dyadic intervention for PO-MDD, PCIT-ED, compared to a WL control condition.

Hypothesis 1A: Compared to those randomized to the WL, preschoolers who are first randomized to PCIT-ED will show significantly increased rates of remission, greater reductions in MDD symptoms, and decreases in impairment.

Hypothesis 1B: Compared to those randomized to the WL, preschoolers who are first randomized to PCIT-ED will show significantly greater increases in emotional competence measured by the ability to accurately identify emotions in themselves and others and the ability to effectively regulate intense emotions.

Hypothesis 1C: Compared to those on the WL, parents who are first randomized to PCIT-ED will show significantly greater increases in emotion skill learning (ESL) and reductions in MDD symptoms and parenting stress.

Analytic Approach: Continuous post-assessment scores will be compared between PCIT-ED and WL groups using analysis of covariance, covarying for pre-assessment scores. The stratification variables, gender and externalizing comorbid diagnoses, will also be included as covariates in the models.

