To assess parental ESL as a potential mediator of the relationship between treatment group and child treatment response, a macro (for SAS or SPSS) developed by Hayes will be utilized. For mediation analyses, the PROCESS macro estimates path coefficients in a mediation model and generates bootstrap confidence intervals for the indirect effects of the independent variable on the dependent variable through a mediator variable. It is also possible to include covariates not proposed to be mediators in the model. Paternal ESL will be evaluated by entering post ESL score into the model as a potential mediator, with treatment group as the independent variable and change in PAPA MDD severity sum score as the dependent variable.

Power for Mediation: To estimate power for this mediation analysis, the following steps were taken. First, we expect the difference in MDD severity sum change score in the two groups to be approximately 2.5, with a SD of 4.69 (based on our pilot study). With 90 subjects per group, an alpha of 0.05, and a 1-sided test, power=0.97. Next, we expect the correlation of change in MDD severity sum score and ESL score to be approximately 0.25. Using Fisher's Z transformation with a sample size of 180, the correlation of 0.25 transforms to $Z = \tanh(0.25) * \sqrt{180-3} = 3.398$. Subtracting 1.96 gives 1.438, corresponding to power=0.92. Thus, we will be well-powered to detect a mediation effect.

To assess parental emotional intelligence (EI) as a potential moderator of treatment response, the PROCESS macro will be used. For moderation analyses, the PROCESS macro

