Hypothesis 3: MDD remission (not meeting diagnostic criteria for ≥ 2 weeks) will be sustained at the 18 week follow-up in 80% of subjects who were in remission at the post-treatment assessment.

Analytic Approach: Rate of 18 week remission in subjects who met remission requirements at the post assessment will be calculated and compared to the 80% expected rate using a Chi-square goodness-of-fit test.

General Data Analysis Considerations: All outcome measures other than MDD diagnosis are continuous. The PFC-Scale and MDD severity scores from our pilot PCIT-ED and DEPI subjects were approximately normally distributed, as determined by the Shapiro-Wilk test. However, if these scores or other outcome scores are found to be from non-normal distributions, the data will be log- or power-transformed prior to analysis. Bonferroni correction will be used to limit the possibility of Type I errors for the main outcomes. A less conservative correction, such as the Bonferroni-Holm correction, will be applied for tests of other outcomes.

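### The mediation power of 0.92 is power for a single ESL-outcome correlation, not for the planned bootstrap test of the indirect effect, so power for the mediation aim is not established

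*Combined protocol and SAP*

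**What the plan says.** In the SAP, Specific Aim 2, Analytic Approach, mediation is to be tested with the PROCESS macro, which "generates bootstrap confidence intervals for the indirect effects of the independent variable on the dependent variable through a mediator variable". Post-treatment ESL is the mediator, "with treatment group as the independent variable and change in PAPA MDD severity sum score as the dependent variable". On adjustment, the text says only: "It is also possible to include covariates not proposed to be mediators in the model". It does not say which type of bootstrap interval will be used.

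The Power for Mediation paragraph has two steps:

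- Total treatment effect: a difference of 2.5 with SD 4.69. "With 90 subjects per group, an alpha of 0.05, and a 1-sided test, power=0.97".
- ESL-outcome association: "we expect the correlation of change in MDD severity sum score and ESL score to be approximately 0.25". This is converted by Fisher's Z with N=180 to 3.398.

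The paragraph then concludes: "Subtracting 1.96 gives 1.438, corresponding to power=0.92. Thus, we will be well-powered to detect a mediation effect".

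Hypothesis 1C (Specific Aim 1) expects parents in PCIT-ED to gain more ESL than those on the wait list (WL), but gives a direction and no size. The only ESL means in the plan, 2.1 and 2.5 under Power for Moderation, are for high- and low-EI subgroups within PCIT-ED, not for PCIT-ED versus WL.

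**The concern.** The planned test concerns the product a × b. Here a is the effect of treatment on post ESL, and b is the association of ESL with MDD change after adjustment for treatment. Neither power step addresses that product. The total effect is not a component of a × b, and a correlation tested without a treatment term is not b. Path a has no assumed size anywhere in the plan.

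Two smaller points add to the uncertainty. The plan does not say whether 0.25 is pooled over arms or within arm, and the two readings imply different values of b. The two steps also mix a one-sided test with a two-sided critical value.

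What is at stake is the reading of Hypothesis 2A. If the indirect effect is not significant, the plan as written invites the conclusion that a test with more than 90% power found no mediation by ESL. That power has not been shown.

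**Working it through.** **1. The plan's own figures.** Inputs are from Power for Mediation.

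- Total effect: 2.5 / (4.69 × √(2/90)) = 3.576. One-sided power is Φ(3.576 − 1.645) = 0.97, as stated; two-sided it is about 0.95.
- Correlation: atanh(0.25) × √177 = 3.398; 3.398 − 1.96 = 1.438; Φ(1.438) = 0.925, against the stated 0.92. (The formula is printed with tanh, but the value 3.398 requires its inverse.)

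Both figures reproduce. The second is exactly a test of one correlation with no treatment term.

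**2. What the planned test needs.** Let X be treatment, M post ESL and Y MDD change.

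- From the plan: d = 2.5/4.69 = 0.533, so r_XY = d/√(d² + 4) = 0.2575.
- Not in the plan: r_XM (path a). It is scanned here as an assumption; in SD units the arm difference in ESL is 2·r_XM/√(1 − r_XM²).
- If 0.25 is pooled, the correlation given treatment is (0.25 − 0.2575·r_XM)/√((1 − 0.2575²)(1 − r_XM²)).
- If 0.25 is within arm, the correlation given treatment is 0.25 throughout.

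Joint-significance power is the Fisher-z power for a (N − 3) times that for b (N − 4), with N=180 and two-sided 0.05. At r_XM = 0.20, for example, power for a is 0.769. On the pooled reading the adjusted correlation is 0.210 and power for b is 0.806, giving 0.769 × 0.806 = 0.62.

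The bootstrap columns are simulations of the interval for a × b (2,000 replicates × 1,000 resamples, Monte Carlo SE up to 0.011), without covariates. BC means bias-corrected.

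| r_XM (assumed) | ESL difference, SD | Pooled: joint | Pooled: percentile | Pooled: BC | Within-arm: joint | Within-arm: percentile | Within-arm: BC |
|---|---|---|---|---|---|---|---|
| 0.10 | 0.20 | 0.235 | 0.248 | 0.342 | 0.246 | 0.239 | 0.321 |
| 0.20 | 0.41 | 0.620 | 0.617 | 0.716 | 0.711 | 0.720 | 0.800 |
| 0.27 | 0.56 | 0.710 | 0.718 | 0.785 | 0.884 | 0.887 | 0.918 |
| 0.30 | 0.63 | 0.700 | 0.697 | 0.759 | 0.909 | 0.914 | 0.940 |
| 0.33 | 0.70 | 0.677 | 0.679 | 0.734 | 0.919 | 0.925 | 0.946 |
| 0.50 | 1.15 | 0.490 | 0.491 | 0.515 | 0.923 | 0.922 | 0.933 |

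**3. Why a large ESL effect does not settle it.** On the pooled reading a stronger path a leaves less ESL-outcome association once treatment is in the model. The adjusted correlation falls from 0.210 to 0.187 to 0.145 as r_XM goes from 0.20 to 0.30 to 0.50. Power for b falls with it, from 0.81 to 0.71 to 0.49. Joint power therefore peaks at 0.71 (r_XM = 0.27) and then declines.

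**4. Covariates and interval type.** Suppose covariates remove 15% or 25% of residual outcome variance and are unrelated to ESL (an assumption). Pooled power at r_XM = 0.30 then becomes 0.772 or 0.824 (percentile) and 0.820 or 0.868 (BC), so 0.71 is not a ceiling.

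The BC interval gains power partly through a higher type I error. In 4,000 simulated trials with b = 0 and r_XM = 0.27, the error was 0.052 (percentile) against 0.080 (BC). With a = 0 and b = 0.25 it was 0.045 against 0.074.

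**The case against.** The strongest reply is that power may well be adequate. If 0.25 is a within-arm correlation, the 0.92 is in effect the power for path b. The ED module trains parents directly in emotion skills and the comparator is an untreated wait list, so path a could be large. Joint power would then be about 0.91 to 0.92 from a treatment-ESL correlation of 0.30 upward. On this view the low values in the scan, such as 0.10 (0.2 SD), are a pessimistic reading of the design.

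This stands as far as it goes, and it is why the conclusion is that power is not established rather than that it is too low. It does not rescue the statement in the plan. The within-arm reading is not stated, and the formula used (180 subjects, N − 3, no treatment term) looks like a pooled correlation. On the pooled reading a larger path a eventually lowers power.

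It can also be said that the interval type and covariates are side issues and that the consequence is limited, since a reported confidence interval would itself show how imprecise a null result is. The limited consequence is accepted. The interval type and covariates are needed only because power for this test cannot be computed without fixing them.

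**Conclusion.** The concern holds. The stated 0.92 is correct arithmetic for a test that is not the planned one, and the claim of being well powered for mediation does not follow from it.

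No single replacement figure can be given, because the plan fixes neither the PCIT-ED versus WL difference in ESL nor the meaning of 0.25. Without covariates, the percentile interval matches the stated 0.92 only if 0.25 is within arm and the ESL difference is about 0.7 SD or more; the bias-corrected interval gets there at about 0.56 SD. On the pooled reading, no scanned value without covariates reaches 0.80 with either interval. At a treatment-ESL correlation of 0.20 (0.41 SD), power without covariates is about 0.80 at most on any version. All of this rests on the assumed range for path a, normally distributed data and 180 analysed subjects.

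The point is confined to the justification for Aim 2. The sample size was set by the Aim 1 comparison, which is untouched, and the mediation estimate is not biased by it. It should be corrected before the mediation result is interpreted.

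**What to change.** Replace the two calculations with one simulation of the planned bootstrap test of a × b at N=180. State in the SAP:

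- the assumed PCIT-ED versus WL difference in ESL, with a range if the pilot does not fix it (General Data Analysis Considerations names the pilot groups as PCIT-ED and DEPI, so a WL contrast may not be available);
- the ESL-outcome association given treatment, and whether 0.25 is pooled or within arm;
- the type of bootstrap interval;
- any covariates in the mediation model;
- one choice of sidedness, used throughout.

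Report the resulting power, over the range where inputs are uncertain, and delete the well-powered statement unless the simulation supports it.

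The cost is one simulation and a rewritten paragraph; the plan already simulated data and ran PROCESS for its moderation power. No extra data or participants are needed. The stated power may turn out less favourable.

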PFC-Scale and PAPA MDD severity sum scores will be used to assess differences in depressive symptoms; HBQ and PAPA impairment scores will be analyzed to determine differences in functional impairment. Differences in emotion regulation (as an executive function) in the two groups will be examined using scores from the BRIEF-P; emotion development will be analyzed using scores from the ERC, Emotion Understanding, FACE, KIDSEDF, and the "Waiting" and "Puzzle" tasks. Post-assessment EDCl, BDI-II, and PSI scores will be compared between PCIT-ED and WL groups to determine differences in increases in Emotion Skill Learning and reduction of parental depressive symptoms and parenting stress.

Rates of remission (defined by 50% reduction in MDD severity and not meeting diagnostic criteria) will be compared in the PCIT-ED and WL subjects using logistic regression.

Interval assessment scores will also be analyzed across PCIT-ED and WL groups in repeated measures mixed models. In these models, repeated measures of PFC-Scale, HBQ MDD and externalizing co-morbidity severity and impairment, PSI and ESL (measured by EDCl) at pre-assessment, 6-week assessment, 12-week assessment, and post-assessment will be compared between the PCIT-ED and WL groups.

In addition to the analyses described above, pre-assessment variables that could possibly be associated with outcome, such as subject age and maternal depression, will be investigated as potential predictors of outcome.

Specific Aim 2: To investigate mediators and moderators of treatment effects.

Hypothesis 2A: Parental emotion skill learning (ESL) will mediate treatment effects. Child depression outcomes will be mediated by parental ESL.

Hypothesis 2B: Parental Emotional Intelligence (EI, a stable trait measured at baseline by MSCEIT) will be a moderator of ESL and child outcome. Parents with higher EI will show better ESL, and as a result, children of parents with high EI will show better outcomes than children of parents with low EI.

Analytic Approach: Parental ESL will be measured with the Emotion Development Coding instrument. This is an itemized assessment of parents' emotion skill learning. Each item is rated as 3=satisfactory, 2=needs practice, or 1=not evident. The total ESL score will be calculated as the mean of these items.

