estimates a moderation model with the effect of the independent variable on the dependent variable moderated by a proposed moderator variable. The independent variable (ESL score) and proposed moderator variable (pre-assessment parental EI) are centered to eliminate any multicollinearity effects. The macro generates the conditional effects of ESL score on the dependent variable (MDD severity sum score) at values of EI score equal to selected percentiles (e.g., 10th, 25th, 50th, 75th, and 90th percentiles) of the distribution in the sample. The Johnson-Neyman technique will be used to identify the values of EI score at which point the effect of ESL score changes from statistically significant to statistically non-significant. If EI score is found to be a significant moderator, the independent and moderator variables (ESL score and pre-assessment EI score) will be dichotomized so that all subjects fall into 1 of 4 categories (low ESL with low parental EI, low ESL with high parental EI, high ESL with low parental EI, and high ESL with high parental EI). Post-hoc pair-wise comparisons of treatment outcome in these 4 groups will be conducted.

Power for Moderation: To estimate power for this moderation analysis, a simulated dataset of 90 PCIT-ED subjects was created. This dataset contained variables for parental ESL, parental EI, and change in MDD severity sum score. Random data was generated for 45 “high EI” subjects and 45 “low EI” subjects assuming normally distributed data for each of these variables, with SD’s based on our pilot study (SD=0.22 for ESL, SD=15.6 for EI, SD=4.69 for MDD change score). The mean scores for the random normally distributed data varied in the two groups as we expect it to in the proposed study. For the “high EI” group, assumed means were 2.1 for ESL, 118 for EI, and -6.5 for MDD change. For the “low EI” group, assumed means were 2.5 for ESL, 99 for EI, and -1 for MDD change. Running the PROCESS macro on the simulated dataset yielded a significant interaction of ESL and EI, with a coefficient=0.2440 and SE=0.0758. Subtracting 1.96 from the corresponding t score (3.219) gave Z=1.259, which corresponds to power=0.90.

Specific Aim 3: To investigate whether reductions in depressive symptom severity and diagnostic remission is sustained 18 weeks after treatment has ended in those randomized to PCIT-ED first.

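### Aim 2 promises a test of whether parental EI changes the effect of PCIT-ED, but its only moderation model is ESL × EI with no treatment-group term

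*Combined protocol and SAP*

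**What the plan says.** The SAP sets the aim as "Specific Aim 2: To investigate mediators and moderators of treatment effects". Under it, Hypothesis 2B says that parental EI, measured at baseline, "will be a moderator of ESL and child outcome"; that clause does not mention treatment group. The Analytic Approach introduces the moderation analysis with "To assess parental emotional intelligence (EI) as a potential moderator of treatment response, the PROCESS macro will be used".

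The model is then specified: "The independent variable (ESL score) and proposed moderator variable (pre-assessment parental EI) are centered to eliminate any multicollinearity effects". The effect to be probed is that of ESL: "The macro generates the conditional effects of ESL score on the dependent variable (MDD severity sum score) at values of EI score". The Johnson-Neyman step and the four post-hoc groups are also defined by ESL and EI. Within Aim 2, treatment group enters only the mediation model, "with treatment group as the independent variable and change in PAPA MDD severity sum score as the dependent variable".

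For the power calculation, "a simulated dataset of 90 PCIT-ED subjects was created", half high EI and half low EI, and power is given as 0.90. No treatment group × EI test appears anywhere in the plan.

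**The concern.** A moderator of a randomized treatment effect is a baseline characteristic across which the PCIT-ED minus WL difference varies. Testing for one needs both arms and a treatment group × EI term. The planned model asks something else: whether the slope of child outcome on ESL depends on EI. ESL is measured after randomization, and Hypothesis 1C expects PCIT-ED to raise it.

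Two errors could follow. Real variation of the treatment effect with EI could go undetected, because nothing in the model estimates it. Or a real ESL × EI association could be reported, under the Aim 2 heading, as evidence about which families benefit from PCIT-ED, although the randomized contrast was never examined.

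**Working it through.** **1. The plan's own power figure.** From Power for Moderation: coefficient 0.2440, SE 0.0758.
- t = 0.2440 / 0.0758 = 3.219
- 3.219 − 1.96 = 1.259
- Φ(1.259) = 0.896, which agrees with the stated 0.90.

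This is power for ESL × EI within one arm. It says nothing about treatment group × EI.

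**2. What each model can detect.** Simulation with 90 per arm, residual SD 4.69 (the plan's figure), ESL SD 0.22 and 4,000 runs per scenario. EI has mean (118 + 99)/2 = 108.5 and SD √(15.6² + 9.5²) ≈ 18.3, from the plan's EI means and SD. The effects below are assumed, because the documents give none for treatment group × EI. The planned model is fitted in PCIT-ED and the arm × EI model in both arms.

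| Assumed truth | Planned ESL × EI rejects | Arm × EI rejects |
|---|---|---|
| Treatment effect varies by 2.75 points per SD of EI; no ESL × EI effect | 5% | 96% |
| Treatment effect constant at 2.5 points; ESL × EI coefficient 0.244 in both arms | 47% | 6% |

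In the first row the planned test does no better than its false-positive rate. In the second it is often significant although the treatment effect does not vary with EI.

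**3. Power for the missing test.** Inputs: 90 completers per arm and SD 4.69 (SAP). Assumptions: EI split at the median, 45 per arm-by-EI cell, two-sided alpha 0.05, normal approximation.
- SE of the 2 × 2 contrast = 4.69 × √(4/45) = 1.398
- Power = Φ(d/1.398 − 1.96) + Φ(−d/1.398 − 1.96)

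| Difference in treatment effect, high versus low EI (d, points) | Power |
|---|---|
| 1.25 | 0.15 |
| 2.5 | 0.43 |
| 3.75 | 0.76 |
| 5.0 | 0.95 |
| 5.5 | 0.98 |

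- Detectable difference at 80% power: (1.96 + 0.8416) × 1.398 = 3.92 points
- At 90% power: (1.96 + 1.2816) × 1.398 = 4.53 points

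**4. What those differences mean against the plan's 2.5-point overall effect.** With equal EI halves, a 3.92-point difference puts the benefit at 2.5 + 1.96 = 4.46 points in one half and 2.5 − 1.96 = 0.54 in the other. For 5.5 points, take the plan's PCIT-ED means (−6.5 and −1, average −3.75). A 2.5-point overall effect then puts WL at −1.25. If WL shows no EI gradient, the effects are −6.5 + 1.25 = −5.25 in high-EI families and −1 + 1.25 = +0.25 in low-EI families. The 0.98 therefore belongs to a case in which low-EI families gain nothing.

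**The case against.** The best defence is that Hypothesis 2B governs the analysis, and its wording concerns EI, ESL and child outcome. The ESL × EI model fits that. The SAP also uses the phrase treatment response in the mediation paragraph simply for the child's outcome, so the sentence introducing the moderation analysis need not refer to a between-arm difference. Both points stand, and they are why the ESL × EI model should be kept. They do not dispose of the Aim 2 statement, which refers to treatment effects and is served by no test in the plan.

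A reader might go further in three ways that the documents do not support.

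- *That a purely prognostic EI effect would be reported as moderation.* The 5.5-point gap between the assumed PCIT-ED means is an EI main effect, whereas the planned test is the product term. Simulating the plan's own PCIT-ED means and SDs, with the variables independent within EI group, the product term rejects about 5% of the time (4.7% in 20,000 runs). Prognosis alone does not trigger it; a real ESL × EI association is needed. What this implies for the 0.90 itself is a separate matter.
- *That the analysis is confined to PCIT-ED.* That restriction is explicit only for the power simulation; the analysis text names no arm. Pooling the arms would not rescue the model. With no arm term, ESL would partly stand in for arm, and an arm main effect alone would still not supply the interaction.
- *That the right test is comfortably powered at 180.* The documents give no WL means by EI, so every such figure depends on an assumed gradient.

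**Conclusion.** The concern holds in a limited form. The planned model can address Hypothesis 2B as worded, but it cannot show whether the PCIT-ED minus WL difference varies with EI, which is what Aim 2 promises. The stated 0.90 does not apply to that question. Under the median-split assumptions above, 180 completers give 80% power only for a difference of about 3.9 points, which exceeds the plan's overall effect of 2.5. The rejection rates in step 2 rest on assumed effects; they show the kind of error possible, not its likelihood in this trial.

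This should be fixed, but it touches one analysis within Aim 2. The Aim 1 comparisons, the mediation model (which includes treatment group) and Aim 3 are unaffected.

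**What to change.** Add to Aim 2 a treatment group × baseline EI interaction, with EI continuous and centered, in all randomized children. The outcome should be post-assessment MDD severity, adjusted for pre-assessment severity, gender and externalizing comorbidity, as in the Aim 1 models. Report the PCIT-ED minus WL difference across the range of EI. Keep ESL × EI for Hypothesis 2B, state which arms it uses, and do not describe it as moderation of the treatment effect.

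State that the 0.90 does not carry over, and give the detectable difference for the added test with its assumptions. The median-split figures are a guide only, since the fitted model is continuous in EI and baseline-adjusted.

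If the test is not added, the minimum is to reword Aim 2 and the sentence introducing the moderation analysis so that they claim only an association between ESL and outcome that may depend on EI. A moderated-mediation model that includes treatment group is another route that keeps ESL.

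The cost is SAP wording and one extra model. EI is measured at baseline and randomization follows the baseline assessment, so no new data are needed. The price is an openly acknowledged limit: moderate treatment moderation would probably be missed, and a null result should not be read as its absence.

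### Hypothesis 2B predicts that parental EI acts through ESL, but the only analysis named for EI is an ESL × EI interaction, which does not test that prediction

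*Combined protocol and SAP*

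**What the plan says.** Hypothesis 2B (SAP, Specific Aim 2) has two sentences. The first says that EI, measured at baseline, "will be a moderator of ESL and child outcome". The second gives the directional prediction: "Parents with higher EI will show better ESL, and as a result, children of parents with high EI will show better outcomes" than those of low-EI parents.

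The Analytic Approach under Aim 2 names one model for EI, a PROCESS moderation model with MDD severity as the dependent variable. In it, "The independent variable (ESL score) and proposed moderator variable (pre-assessment parental EI) are centered". The ESL effect is then read at percentiles of EI, with the Johnson-Neyman technique. A four-group comparison of treatment outcome (low or high ESL by low or high EI) follows only "If EI score is found to be a significant moderator".

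The mediation model under the same aim takes post ESL as mediator, "with treatment group as the independent variable and change in PAPA MDD severity sum score as the dependent variable". Under Aim 1, pre-assessment variables "such as subject age and maternal depression, will be investigated as potential predictors of outcome"; EI is not among the examples. For the power of the moderation analysis, "a simulated dataset of 90 PCIT-ED subjects was created", and the stated power is 0.90.

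**The concern.** The second sentence of 2B describes a chain: EI raises ESL, and ESL improves the child's outcome. That is an indirect effect, and it has two testable links. The interaction model asks something else, namely whether the slope of outcome on ESL differs by EI. Either can be true without the other.

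At stake is whether the trial can answer its own prediction. A non-significant interaction would leave the chain unexamined. A significant one would show that ESL matters more for some parents than for others, but not that high-EI parents acquired more skill. If the chain is tested only after the data have been seen, the result is post hoc.

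**Working it through.** **1. The plan's own figure.** The SAP reports an interaction coefficient of 0.2440 with SE 0.0758. Then t = 0.2440/0.0758 = 3.219, and Φ(3.219 − 1.96) = Φ(1.259) = 0.896, which reproduces the stated 0.90.

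That is one simulated dataset. Repeating the exercise 20,000 times with the stated group means and SDs (45 + 45, variables taken as independent within group, which the SAP does not state) gives a mean interaction coefficient of −0.0015 and a rejection rate of 4.9%. The stated inputs also give the high-EI group the lower ESL (2.1 against 2.5), opposite to 2B. The 0.90 is therefore no evidence that the planned test suits the prediction.

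**2. Which planned analysis could test the chain?**

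| Planned analysis | Response | Predictor of interest | Tests EI → ESL? | Tests EI → ESL → outcome? |
|---|---|---|---|---|
| Aim 1, ANCOVA | Post ESL, among others | Treatment group | No | No |
| Aim 1, mixed models | ESL over four assessments, among others | Treatment group | No | No |
| Aim 1, predictors of outcome | Outcome | Pre-assessment variables, EI not named | Not named | No |
| Aim 2, mediation | Change in MDD severity | Treatment group, through post ESL | No | No |
| Aim 2, moderation | MDD severity | ESL, EI, ESL × EI | No | No |
| Aim 2, four groups (conditional) | Treatment outcome | ESL and EI, dichotomised | No | No |

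**3. Why the interaction is silent under a linear chain.** In standardised form let ESL = a·EI + e₁ and Y = b·ESL + e₂, where Y is MDD change. Then E[Y | ESL, EI] = b·ESL. In a model with ESL, EI and ESL × EI, the true coefficients are b, 0 and 0. The interaction test rejects at its nominal 5% whatever a, b and N are.

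**4. Size at n = 90.** Inputs:

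- n = 90, from the SAP's moderation power paragraph.
- Size of b = 0.25, the ESL–outcome correlation expected in the mediation power paragraph; 0.35 is assumed.
- a = 0.35 or 0.50, assumed, since the documents state no EI–ESL correlation. The size 0.35 agrees with the SAP's group figures. The covariance from the group means is ¼ × (2.1 − 2.5) × (118 − 99) = −1.90. The variances are 0.22² + ¼ × 0.4² = 0.0884 for ESL and 15.6² + ¼ × 19² = 333.6 for EI. So r = −1.90/√(0.0884 × 333.6) = −0.35. The sign is opposite to 2B; only the size is used here.

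All tests are two-sided at 0.05, unadjusted. The interaction and joint columns rest on 3,000 datasets per row; EI → ESL on 5,000; the ESL main effect on 4,000.

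| a / b | ESL × EI rejects | EI → ESL | ESL main effect in planned model | Both links significant |
|---|---|---|---|---|
| 0.35 / −0.25 | 5.2% | 93% | 59% | 56% |
| 0.35 / −0.35 | 4.4% | 93% | 89% | 83% |
| 0.50 / −0.35 | 5.3% | >99% | 84% | 84% |

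Hand check of the first link at a = 0.35: atanh(0.35) × √(90 − 3) = 0.3654 × 9.327 = 3.41, and Φ(3.41 − 1.96) = 0.93.

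**5. Sensitivity.** A separate simulation (6,000 datasets per setting) used a = 0.25 or 0.50, b = 0.25 or 0.50 in size, and N = 90 or 180. The interaction rejected in 4.7% to 5.6% of datasets in all eight settings. Joint power at N = 90 was 42% for 0.25/0.25, 53% for 0.50/0.25, 66% for 0.25/0.50 and 99% for 0.50/0.50. At N = 180 with b = 0.25 it was 84%.

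**The case against.** The strongest defence is that the first sentence of 2B calls EI a moderator, Aim 2 covers moderators, and the SAP introduces the EI analysis as moderation. The ESL × EI model is a natural analysis for that sentence. This stands: the model is not wrong, and it should stay.

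Four stronger readings are tempting, and the documents do not support them.

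- **The planned test fails whenever 2B is true.** The 5% result assumes a chain with no effect modification. If EI both moderates the ESL effect and acts through ESL, the interaction is not zero.
- **No planned analysis has ESL as an outcome.** Aim 1 compares ESL between treatment groups, by ANCOVA and in mixed models. What is missing is ESL as the response with EI as predictor. The predictors-of-outcome sentence is open-ended and might be stretched to cover this, but it does not name EI and does not specify a model.
- **The planned model carries no signal under a chain.** Its ESL main effect does, with 59% to 89% power in the settings above. But the plan does not judge 2B by that term, and it says nothing about whether EI improves ESL. Nor does the plan judge 2B by the EI coefficient given ESL, so its null behaviour under a chain is not a failure of a planned test.
- **The trial would report that EI plays no role.** The SAP states no conclusion to be drawn from a null interaction.

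**Conclusion.** The point holds in this form: the second sentence of 2B predicts an indirect effect that no named analysis tests, and the interaction test cannot stand in for it. That the analyses are absent rests on the text alone. That the interaction rejects at about 5% rests on a linear chain without effect modification, and then holds at any N.

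The joint-link power of about 55% to 85% at n = 90 rests on the assumed EI–ESL correlation and, at the upper end, on an assumed ESL–outcome effect. The 0.50/0.25 combination gives 53%, slightly below that range, and a weaker EI–ESL link of 0.25 with b = 0.25 gives 42%. Joint significance of the two links serves here as a stand-in for the bootstrap interval.

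Severity is moderate. One hypothesis within Aim 2 is affected; Aims 1 and 3 and Hypothesis 2A are not.

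**What to change.** Keep the ESL × EI moderation test as the analysis of the first sentence of 2B. Prespecify beside it, in treated families:

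1. a regression of post ESL on baseline EI;
2. a bootstrap confidence interval for the indirect effect of EI on MDD change through ESL, from the PROCESS macro already named, with EI as independent variable and ESL as mediator.

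State which result bears on which sentence of 2B, and place both additions in the SAP's multiplicity correction. Redo the power for 2B with ESL means that run in the hypothesised direction, and for the interaction with a generating model that contains one.

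The cost is SAP wording and a little more computing on data already to be collected. The statistical price is one or two more tests in the family. For example, if Holm's first step is taken over three tests, the threshold is 0.05/3 = 0.0167 (z = 2.39), and power for the first link at a correlation of 0.35 falls from 93% to Φ(3.41 − 2.39) = 85%. Power for the indirect effect is modest even before adjustment, so a null result there should be reported with its interval and not read as absence of an effect.
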